4.3 Enrollment and Randomization

Eligible patients, who have given written, informed consent and meet all inclusion with no exclusion criterion will undergo 1:1 randomization in an unblinded, parallel arm treatment format to a strategy of drug therapy for rate or rhythm control vs. catheter ablation. Randomization will be accomplished by telephone or internet using a centralized, interactive voice and web

randomization system (IXRS). The enrollment scheme is based on permuted block randomization with stratification by clinical site.

4.4 Post Randomization Procedures

For morbidity and mortality end points, intention-to-treat analysis will begin at randomization. All therapies will be established and optimized in a 3-month treatment initiation period, during which patients may receive alternative drugs or undergo repeat ablation if AF recurs. The duration of this “blinking period” is derived from standard clinical practice and the AF Ablation Consensus Document [50, 51]. Thereafter, therapy will be administered and patients followed for an average of approximately 5 years. Efficacy, (i.e. absence of AF recurrence) will be established by long-term follow-up beginning after the 3-month therapy initiation phase. Any AF occurring after the 3-month blinking period will be considered a treatment failure for the AF recurrence secondary endpoint. Patients will be followed at 6 and 12-month intervals from randomization throughout the trial.

4.4.1 Baseline Testing

Defining the eligibility of patients for the CABANA Trial will require information generated during the course of routine clinical care as dictated by their attending physician. This information should be, consistent with established guidelines, consensus documents, and good clinical practice. Selected baseline testing data will be collected in order to characterize the type, cause and severity of the patient’s AF and the treatments received prior to enrollment. The baseline data will include information from the following clinical evaluations:

1. Relevant medical history including prior and current drug treatment of AF
2. Relevant physical examination
3. 12 lead ECG prior to treatment
4. Blood Tests (INR, creatinine, hemoglobin / hematocrit) (pre-treatment)
5. Trans-thoracic 2-D echocardiography

The trans-thoracic echocardiographic (TTE) data will be used to characterize the substrate underlying the patient’s AF, establishing the presence of LV dysfunction (LVEF), hypertrophy, diastolic dysfunction, or other structural abnormalities. The TTE will also assess LA size and volume, and provide measures of atrial function.

Following a recommended approach consistent with established guidelines, consensus documents, and good clinical practice, a trans-esophageal echocardiographic (TEE) study will be performed within 24 hours prior to ablation in patients with *persistent or longstanding persistent* AF. The TEE may be performed up to 48 hours before the procedure in patients on continuous anticoagulation therapy, such as warfarin at a therapeutic INR or in those appropriately bridged with intravenous un-fractionated or low molecular weight heparin.

The performance of a pre-treatment TEE in patients with *paroxysmal* AF is left to the discretion of the investigator (5.4.4), but is not required in CABANA. Data on the performance and results of all TEEs performed as part of routine care will be collected in the eCRF, however. TEE data may also be used to confirm atrial size and morphology. The approach to cardioversion in drug treated patients should follow the recommendations of AF Treatment Guidelines [92].

In those centers where routine clinical practice includes the performance of pre-ablation and post-ablation CT/MR studies, relevant data from these studies will be collected to serve as a baseline for comparative quantitative LA size, morphology, and function studies, as well as

subsequent follow-up PV and esophageal investigations. In addition at those centers, up to 150 patients randomized to drug therapy will be asked to undergo one research CT/MR scan prior to initiating therapy. This will allow the CABANA study to evaluate and compare atrial structure and function in response to drug or ablative therapy. These drug-treated patients will be recruited from selected centers that are committed to CT/MR assessment of all enrolled patients (both study arms). Since randomization is performed (stratified) within each site, this component of the study will still benefit from the overall study randomization. Optimally, the pre-therapy scans performed in all patients should be within 4 months prior to treatment.

In addition to these clinically dictated studies, baseline economic and QOL data will be obtained after informed consent is obtained, but before randomization occurs.

4.4.2 Patient Follow Up

Follow-up in all patients will occur at 3, 6, and 12 months following randomization during the first year and every 6 months thereafter, with clinic visits, phone follow-up, and other testing as described below. Economic and QOL data, including a full follow-up questionnaire of validated scales, ie, SF-36, DASI, Toronto Atrial Fibrillation Severity Scale, AF Effects on QOL (AFEQT), Work Productivity and Activity Impairment Instrument (WPAI), Stanford Presenteeism scale, will be repeated by trained telephone interviewer staff from the EQOL Coordinating Center (EQOL CC) for patients enrolled in North America and by the Site Coordinator in sites outside North America.

Follow-up visits/calls at 3 and 6 months should be completed within 30 days +/- of the due date (Ex: 3 month visit: completed between 60 days and 120 days of randomization).

Follow-up visits/calls at 12 months and every 6 months thereafter should be completed within 60 days +/- of the due date (Ex: 12 month visit: completed between 300 days and 420 days of randomization).

Medical bills for patients enrolled at US sites will be collected throughout the trial by the EQOL Coordinating Center economic team. The Site Coordinators will complete a one page Rapid Report Form (RRF) at each CABANA study visit documenting any interim hospitalizations and/or ER visits since last contact. These forms will be forwarded to the EQOL Coordinating Center for processing. As part of the economic and QOL data in CABANA, two EQ-5D forms that rate the patient's health by using a 0-100 "thermometer", asking 5 brief questions and Mayo Atrial Fibrillation Symptom Index (MAFSI) will be collected by the Site Coordinator at 3 and 12 months following randomization during the first year and yearly thereafter throughout the trial and entered into the e-CRF.

After enrollment, subjects will either receive a single 'CABANA Box' recording system to be used throughout the entire study, or will be followed using ambulatory event and Holter ECG monitoring as generated during the course of routine clinical care as dictated by their attending physician.

At sites where the 'CABANA Box' has received appropriate approval, all patients enrolled will receive a single 'CABANA Box' recording system to be used for both patient activated event monitoring (throughout the trial), 24 hour autodetect/autocapture (AD:AC) event monitoring and 96 hour full disclosure Holter monitoring throughout the study. During year one, subjects will be asked to record their heart rhythm each month. After the first year, they will be asked for a 24 hour recording twice a year and a 96 hour recording twice a year. Fingertip recordings as well as AD:AC recordings can be transferred via telephone download from the patient's home to the

CABANA monitoring center. Holter recordings will require downloading of information at the enrolling site for data transfer to the CABANA monitoring center. All recordings will be made available to the enrolling center for use in clinical practice.

Follow up monitoring with an alternative system will be required in centers unable to use the “CABANA Box”.

CT/MR imaging studies will be performed where clinically indicated or otherwise part of routine clinical care on ablation subjects after ablation therapy (between 90 days post ablation and the 6 month follow-up) and as indicated for PV stenosis management throughout the trial. The 150 drug therapy patients that received the CT/MR scan prior to initiating drug therapy, will also undergo one research CT/MR scan after therapy is fully established (between 90 days post drug treatment initiation and the 6 month follow-up). CT/MR data will be electronically transferred to a server at the Mayo Biomedical Imaging Resource, the CABANA Trial Image Analysis Lab. Scans will be anonymized at the site using a software tool provided by the Imaging Center. Each clinical center will also perform standard site radiology evaluation and assessment of the CT/MR images according to the sites’ standard clinical practice.

After completion of the 60 month follow-up, subjects will be asked to extend their participation. If agreed upon, subjects will be asked about their current state of health and any clinical events every 6 months by telephone until the last subject enrolled reaches approximately 36 months follow-up.

Follow-up data will also be obtained at the time of treatment discontinuation, with a crossover in treatment strategy, and at the emergence of any primary or secondary endpoints.

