4.4.3 Schedule of Assessment

Assessments	Baseline	Post Therapy	Mo 3	Mo 6	Mo 12	Mo 18	Mo 24	Mo 30	Mo 36	Mo 42	Mo 48	Mo 54	Mo 60	Extended every 6 months
			(+/-) 30 days		(+/-) 60 days									
Medical history Office visit	X		X		X		X		X		X		X	
Medical history Office visit OR phone follow-up				X		X		X		X		X		X
Review Past/Current Medications	X	X(5)	X	X	X	X	X	X	X	X	X	X	X	X
Physical Exam	X			X		X		X		X		X		
Blood Tests (INR, creatinine, hemoglobin, hematocrit)	X													
12 Lead Electrocardiogram (ECG)	X	X(5)												
Transthoracic 2-D Echocardiogram	X													
Trans-esophageal Echocardiogram (1) (2)	X													

Assessments	Baseline	Post Therapy	Mo 3	Mo 6	Mo 12	Mo 18	Mo 24	Mo 30	Mo 36	Mo 42	Mo 48	Mo 54	Mo 60	Extended every 6 months
			(+/-) 30 days		(+/-) 60 days									(+/-) 60 days
CT/MR Evaluation (1) (3)	X		X(4)											
CABANA Box/Ambulatory Monitor Symptom Event Recording		Throughout the 60 month follow-up periods when Atrial Fibrillation symptoms are present												
CABANA Box/Ambulatory Monitor 24-Hour Holter / AC;FD (monthly during Year 1)	X	Monthly / 1,2,3,4,5,7,8,9,10,11				Every 6 months / 15,21,27,33,39,45,51,57								
CABANA Box/Ambulatory Monitor 96-Hour Holter			X	X	X	X	X	X	X	X	X	X	X	
Economic and QOL Survey SF36, DASL	X		X		X		X		X		X		X	X
Economic and QOL Survey Toronto AF Severity Scale AFEQT, WPAI, Stanford Presenteeism	X			X		X		X		X		X		X
AF Severity/Symptom Check List MAFSI, EQ5D	X		X		X		X		X		X		X	X
Review Adverse Events	X	X(5)	X	X	X	X	X	X	X	X	X	X	X	X

- (1) Ablation therapy subjects;
- (2) Or as warranted throughout trial;
- (3) 150 subjects randomized to Drug Therapy;
- (4) 3 months following therapy initiation = end of blanking period. Or as indicated for PV stenosis
- (5) Hospital discharge or following Drug Therapy initiation

All procedures and laboratory tests during follow-up should be performed whether or not a subject receives treatment according to the protocol.

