5.4.2 Guidelines for Anticoagulation Therapy in Ablation Patients

Anticoagulation before, during, and after the ablative intervention will follow the guidelines of the AF Ablation Consensus Document [50]. Prior to the ablative intervention, patients with persistent and long-standing persistent AF should receive adequate anticoagulation (i.e. at least

one month of warfarin anticoagulation (INRs: 2-3)), or have a TEE excluding intra-atrial thrombus at the time of the intervention. During the ablative intervention, maintaining an ACT between 300 and 400 seconds is strongly recommended. Following the ablative intervention, patients will be started on IV heparin or subcutaneous injections of low molecular weight heparin beginning 4 to 6 hours after all sheaths are removed, and appropriate anticoagulation reinstated the evening of the intervention. Thereafter, low molecular weight heparin is to be maintained until anticoagulated appropriately or standard dose warfarin achieves a target INR of 2 to 3, unless the ablation was performed at a therapeutic INR in patients maintained on warfarin through the ablation. One month following the ablation, dabigatran, rivaroxiban or apixaban may be substituted for warfarin, following recently written guidelines. Three to six months after ablation, warfarin may be replaced by full dose aspirin in patients with a CHADs score ≤ 1 . This would include patients with hypertension without hypertrophy, or those < 65 years of age, providing 1) atrial size and function are normal and 2) there is no symptomatic or asymptomatic AF by standard or full-disclosure monitoring. In those patients with a CHADs score ≥ 2 , adequate anticoagulation is to be continued throughout the trial. Randomization of warfarin discontinuation is precluded by the low post-ablation stroke rates that would require at least 10,000 patients for detecting differences in stroke prevalence. Nevertheless, the characteristics, follow-up monitoring results, and long-term anticoagulation status of ablation patients will be compared to descriptively identify predictors of events and profiles of patients at high risk for warfarin discontinuation. The utility of trans-telephonic, auto-detection / full disclosure, and Holter monitoring, as a future aid in the decision to discontinue anticoagulation will also be critically examined.

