In addition, separate analyses will be performed according to the method used for monitoring AF recurrence. As indicated in Section 6 (Data Sources), rhythm data for many of the patients enrolled in CABANA (approximately 2/3 of the randomized patients) are collected using the “CABANA Box,” a robust rhythm monitoring system provided by Medicomp. The rhythm monitoring data are sent from Medicomp to the Duke Clinical Research Institute (DCRI), where a set of programmed rules are run to determine which rhythms should be submitted to the ECG core lab for review and adjudication. Following core lab review, the adjudicated results are electronically transmitted back to the DCRI. Sites that are not using the “CABANA Box” (generally these are international sites where use of the CABANA Box was not approved) submit rhythm data through a secure portal using the CABANA website, which is then processed and submitted to the core lab for adjudication. Because the CABANA Box data are more comprehensive and more routinely and rigorously collected, separate analyses of recurrent atrial arrhythmias will be performed using (a) patients whose rhythms were monitored using the CABANA Box, (b) all remaining patients (i.e., non-CABANA Box patients), and (c) the pooled group of all patients (with use of CABANA Box as a covariate if justified). In the case of

patients who initially used the CABANA Box and later ceased to provide information via CABANA Box, the analysis will censor that data at the time of last CABANA Box recording. The primary analysis of this endpoint will be the analysis of patients with CABANA Box data because of the more comprehensive collection of that rhythm monitoring information. Analysis which includes non-CABANA Box patients (“b” and “c” above) will be considered supplementary analysis.

Statistical Analysis: First, descriptive summaries of baseline characteristics of subjects receiving their assigned treatment and living to the end of the blanking period in both treatment arms will be presented to determine how comparable the patients in the two arms are for this analysis. Continuous variables will be presented in terms of percentiles (median, 25th and 75th percentiles), while discrete variables will be summarized in terms of frequencies and percentages.

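### For patients without the CABANA Box, the protocol has two rules for rhythm recording, and under one of them the supplementary non-Box and pooled recurrent-AF hazard ratios can reflect how often each arm was recorded

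*Protocol*

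**What the plan says.** **Protocol 4.4.2** gives two statements for patients without the Box. One says they will be "followed using ambulatory event and Holter ECG monitoring as generated during the course of routine clinical care as dictated by their attending physician". The other reads "Follow up monitoring with an alternative system will be required in centers unable to use the" Box, and gives no frequency or duration.

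**Protocol 4.4.3** schedules recordings in rows that name both systems: "CABANA Box/Ambulatory Monitor 24-Hour Holter / AC;FD (monthly during Year 1") and "CABANA Box/Ambulatory Monitor 96-Hour Holter". It also lists symptom event recording throughout the 60 months.

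**Protocol 4.3** describes randomization as unblinded.

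**SAP 9.8** defines recurrence as the first episode of at least 30 seconds after the 90-day blanking period. It says about two thirds of randomized patients use the Box, and analyses (a) Box patients, (b) non-Box patients and (c) "the pooled group of all patients (with use of CABANA Box as a covariate if justified"). Analysis (a) is primary for this endpoint because Box data are collected more rigorously; (b) and (c) are supplementary. Patients who stop using the Box are censored at their last Box recording. No matching rule is given for non-Box patients, so the general last-contact rule in SAP 7.3 would apply.

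**SAP 10** repeats the first-recurrence analysis on treatment in the same three populations.

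**The concern.** A recurrence enters the analysis only if someone records it, and core-lab adjudication cannot recover AF that was never recorded. Under the routine-care sentence, a physician who knows the treatment decides how often to record.

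The protocol gives each arm its own reason to record. In 5.4.2, one condition for replacing warfarin after ablation in lower-risk patients is that "there is no symptomatic or asymptomatic AF by standard or full-disclosure monitoring". In 5.2.1, Holter monitoring is one way to check heart-rate targets on drug therapy. Equal recording therefore cannot be assumed, and the sign of any difference cannot be predicted.

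The planned adjustment does not reach the problem. A Box yes/no covariate compares Box with non-Box patients, whereas the possible imbalance lies between arms inside the non-Box group. A patient recorded rarely but contacted regularly would count as AF-free to last contact. At stake is whether (b), and to a lesser degree (c), can be read as a treatment comparison.

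**Working it through.** The documents state no power, event count or recording count by arm for recurrent AF, so there is no figure of the plan's own to reproduce.

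**1. What the table would require.**
- 24-hour row: months 1-5 and 7-11 (10 recordings), then 15, 21, ..., 57 (8).
- 96-hour row: months 3, 6 and 12 (3 recordings), then every 6 months to 60 (8).
- Year 1 therefore has 10 + 3 = 13 recordings, and each later year 2 + 2 = 4.
- After month 3 there are 15 + 10 = 25.

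For the period after year 1, this matches what 4.4.2 asks of Box patients: "they will be asked for a 24 hour recording twice a year and a 96 hour recording twice a year". A non-Box site can obey the routine-care sentence and still make few of these 25 recordings.

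**2. Group sizes.** The SAP overview gives 2,204 patients. One third is about 735, or 367 per arm without the Box. That leaves about 735 per arm with it.

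**3. Direction and rough size by hand.** Suppose AF returns at a mean of M/ln 2 months (median M), recordings come every Δ months, and each recording after onset detects AF with probability s. The mean delay from onset to detection is Δ(1/s − 1/2). Compare Δ = 6 with Δ = 4, a 1.5-fold difference:
- s = 0.2, M = 6: delays 27 and 18 months, mean onset 8.7. Mean detection times are 35.7 and 26.7, ratio 1.34.
- s = 0.9, M = 24: delays 3.7 and 2.4 months, mean onset 34.6. Mean detection times are 38.3 and 37.1, ratio 1.03.

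The distortion is large when recordings often miss AF or recurrence is early, and small when detection is nearly certain and recurrence is slow.

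**4. Simulation with a true hazard ratio of 1.00.** Assumptions: M from 6 to 24 months; s from 0.2 to 0.9; follow-up uniform from 24 to 60 months, starting after blanking; 367 per arm non-Box; 735 per arm Box, recorded every 2 months in both arms. Cox model, pooled fit stratified by Box use, two-sided 0.05, 300 replicates per setting.

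| Recording, ablation versus drug | Non-Box HR | Rejection | Pooled HR | Rejection |
|---|---|---|---|---|
| Equal (every 6 months) | 1.00 | 3-7% | 1.00 | 2-6% |
| Ablation 1.5 times as often | 1.06-1.46 | 9-99% | 1.02-1.11 | 7-66% |
| Ablation twice as often | 1.08-1.85 | 13-100% | 1.03-1.19 | 7-97% |
| Drug twice as often | 0.54-0.92 | 13-100% | 0.84-0.98 | 8-96% |

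The pooled figures are already stratified by Box use, and the shift remains. It is smaller only because the equally recorded Box patients dilute it.

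**5. Would keeping only recordings near the scheduled months cure it?** After year 1 the combined grid has a recording about every 3 months, and the visit windows are ±60 days. Month 15 (day 456) spans days 396-516 and month 18 (day 547.5) spans about days 487-607, so they overlap. Months 3 to 60 are fully covered. If only visit months count, about 120 of every 182 days still qualify, roughly two thirds. In a separate simulation at 1 versus 1.5 recordings per year, the visit-window filter left the hazard ratio at 1.33-1.34, against 1.27-1.37 unfiltered.

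**The case against.** The strongest reply is that the SAP has already dealt with this by ranking. It says Box data are better, makes the Box-only analysis primary for this endpoint, and labels the other two supplementary. Recurrent AF is one of 13 secondary endpoints. This stands, and it limits the consequence. It does not make (b) and (c) interpretable, and both are still planned, as are their on-treatment versions.

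A second reply is that the 4.4.3 table does cover ambulatory monitors, and 4.4.2 does require an alternative system. This stands in part: a site that followed the table would record both arms alike. But the routine-care sentence remains in force beside it, and the requirement sets no frequency.

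A third reply is that no imbalance has been shown. That is correct. The ablation-arm trigger covers only patients with a CHADS score of 1 or less, from three to six months after ablation. The drug arm has the Holter rate check in 5.2.1 and the sinus-rhythm benchmarking in 5.2.7. A reader might infer that the bias runs against ablation; the documents do not support a direction.

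A reader might also infer that the non-Box analysis is the only recurrence evidence for most international sites. SAP 9.8 says that non-Box sites are generally international, which is not the same as saying that most international sites lack the Box.

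**Conclusion.** The point holds for the non-Box and pooled recurrent-AF analyses in SAP 9.8 and their counterparts in SAP 10. Protocol 4.4.2 and 4.4.3 conflict on whether non-Box recordings follow a schedule. Under the routine-care rule, an arm difference in recording moves the hazard ratio against the arm recorded more. For a 1.5-fold difference the size is about 1.06-1.46 (non-Box) and 1.02-1.11 (pooled), or the reciprocals if the drug arm is recorded more. The lower ends are close to no effect.

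These figures rest on assumed recording ratios, detection probabilities and recurrence times. They show what could happen, not what did. They also leave out symptom-triggered recordings.

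The tempting stronger reading is that the trial's AF-recurrence result, or even its main result, is compromised. The documents do not support that: the primary recurrence analysis uses Box patients only, and the primary endpoint does not depend on rhythm recording. The change should be made, but no primary inference hangs on it.

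**What to change.** **Protocol.** Reconcile the two statements in 4.4.2 with the 4.4.3 table, so that recordings used for the AF endpoint at non-Box sites follow one schedule, the same in both arms. Recordings made for clinical reasons need not be restricted.

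**SAP 9.8 (b) and (c), and the matching SAP 10 analyses.**
1. Tabulate number and hours of recordings by arm, separately for Box and non-Box patients. This alone tells a reader whether the comparison can be trusted.
2. Censor non-Box patients without AF at their last recording, as is already done for patients who stop using the Box. This removes unobserved time at the end of follow-up. It does not by itself remove the effect of unequal frequency.
3. Add a sensitivity analysis that conditions on recording: one recording per scheduled slot (for example the one nearest the scheduled date), modelling AF yes/no by arm among slots with a recording, with standard errors clustered by patient. It assumes that whether a slot has a recording does not depend on AF differently in the two arms.
4. Leave the symptomatic definitions unrestricted, because they depend on symptom-triggered recordings. Do not rely on a scheduled-month filter, which excludes essentially nothing.

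**Cost.** Slightly more analysis work and shorter follow-up for rarely recorded patients, with no new data collection. The SAP describes enrolment as complete, so rewording the protocol cannot change recordings already made. For those, the SAP changes carry the benefit.

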whom it is not possible to obtain both studies (because they die or fail to return for other reasons to enable the follow-up measurements to be made). Every effort will be made to minimize the amount of missing data. However, because some data are expected to be missing, several missing data strategies will be employed in order to assess the sensitivity of the conclusions to the approach used. The approaches that will be considered include (1) analyzing only patients with complete data; (2) assigning “worst case” scores to missing observations; (3) carry forward previously observed data to the observation period missed; and (4) use of likelihood-based methods to impute missing data. By synthesizing the results from these different but complementary approaches, it will be possible to provide a comprehensive assessment with respect to these key mechanistic data.

8.2.5 “On-Treatment” Analysis

Although the intention to treat analyses will serve as the standard for interpreting treatment differences in the key clinical outcomes and constitute the primary analyses in the trial, because a number of patients from the drug arm may cross over to receive ablation during the trial, we will supplement the intent to treat comparisons with “on-treatment” comparisons. The “on-treatment” analysis will involve a comparison of patients who received ablation (even if originally assigned to the drug arm) versus those who did not. Statistically, this will be accomplished using the Cox proportional hazards model with ablation included in the analysis as a time-dependent covariate. Thus, event-free follow-up time for a patient in the drug arm who later crosses over to ablation would be credited to the drug arm until the time of crossover, and at that point, the patient would be shifted to the ablation group. Because treatment assignment is no longer random, results can be biased by an association between the likelihood of treatment change and the risk of a clinical event (i.e., factors that make a patient more likely to cross over may also make them more likely to have an event). Thus such analyses should be cautiously interpreted. The “on-treatment” analyses will also include an assessment of freedom from AF in ablation patients after each ablation performed, including those undertaken after the end of the blanking period.

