covariates between groups, adjustment for covariates will be considered. Secondary analyses will use a paired-sample t-test instead of GLM.

In dealing with this type of data, the completeness of which is dependent on obtaining both the pre- and post-treatment studies, there will inherently be missing data resulting from patients in whom it was not possible to obtain both studies (because they died or failed to return for other reasons to enable the follow-up measurements to be made). The completeness of the data will be fully described, and the statistical comparisons will be based on patients for whom both the baseline and follow-up studies are available.

10. “On-Treatment” Analysis

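### The left atrial imaging comparison is not confined to centers that scan both arms, so it may lose the randomization benefit the protocol claims for it (minor)

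*Protocol*

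**What the plan says.** **Ablation scans.** Protocol 4.4.1 takes data from centers where CT or MR before and after ablation is routine; there, "relevant data from these studies will be collected to serve as a baseline for comparative quantitative LA size, morphology, and function studies". For the post-treatment scan, 4.4.2 states: "CT/MR imaging studies will be performed where clinically indicated or otherwise part of routine clinical care on ablation subjects after ablation therapy". Protocol 5.3.1 goes further. It has every patient randomized to ablation scanned at baseline and makes those scans the basis for the comparison with drug therapy. The 4.4.3 schedule likewise lists CT/MR for ablation subjects generally, but for only 150 drug subjects.

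**Drug scans.** Up to 150 drug-arm patients are asked, after randomization, to have a research scan before treatment, and each "will also undergo one research CT/MR scan after therapy is fully established" (4.4.2). On their source, 4.4.1 says: "These drug-treated patients will be recruited from selected centers that are committed to CT/MR assessment of all enrolled patients", meaning both arms.

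**The claim.** Protocol 4.4.1 adds: "Since randomization is performed (stratified) within each site, this component of the study will still benefit from the overall study randomization".

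**The analysis.** SAP 9.13 covers participants in the imaging sub-study and does not say which ablation patients those are. It fits a general linear model with the baseline value as covariate. If other baseline differences appear between groups, "covariates between groups, adjustment for covariates will be considered". On incomplete data, "the statistical comparisons will be based on patients for whom both the baseline and follow-up studies are available". Protocol 8.2.4 had said that "several missing data strategies will be employed in order to assess the sensitivity of the conclusions to the approach used", and named four: complete cases, worst-case scores, carrying values forward, and likelihood-based imputation.

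**The concern.** Site-stratified randomization protects a sub-study only when both arms of the comparison come from the same sites. The drug side is limited to selected centers. Nothing in SAP 9.13 places the same limit on the ablation side, and no site term is there to absorb the difference. If ablation patients from centers with no scanned drug patient enter, differences between centers in patient mix or scanning practice become part of the apparent treatment effect.

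The SAP also reduces four missing-data approaches to one. A result from patients with both scans would stand alone, although whether a second ablation scan exists can depend on local practice or clinical indication.

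At stake is the last of 13 listed secondary endpoints. Protocol 8.2.4 regards it as important mechanistic evidence, but it has no stated power or confirmatory role.

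**Working it through.** The plan gives no sample size, SD or power for this endpoint, so there is no figure to reproduce. The main check is to compare the texts.

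| Element | Ablation | Drug |
|---|---|---|
| Centers | Routine-scan centers (4.4.1, 4.4.2), or all (5.3.1) | Selected centers scanning both arms (4.4.1) |
| Number | Not capped | At most 150 |
| Reason for follow-up scan | Routine care or indication | Research scan |
| SAP 9.13 center restriction | None | Follows from recruitment |
| SAP 9.13 site term | None | None |

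The 4.4.1 claim needs the first row to match. It matches only if the sub-study means the selected centers for both arms, which SAP 9.13 does not state.

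**How far the two populations could differ.**

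- SAP overview: 2,204 randomized 1:1, so 2,204/2 = 1,102 per arm. The drug cap is 150/1,102 = 13.6% of that arm.
- Let k be the ablation patients at the selected centers. With 1:1 allocation within site, k is about 150 if every drug patient there is scanned, or 300 if half are (assumed).
- Let T be the ablation patients with both scans. T is not given. Assumed: 30% and 70% of 1,102, i.e. 331 and 771, with 1,102 as the ceiling. The ceiling supposes that every ablation patient is scanned twice.
- The share of ablation patients from other centers is s = (T − k)/T.

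| T | k = 150 | k = 300 |
|---|---|---|
| 331 | 181/331 = 55% | 31/331 = 9% |
| 771 | 621/771 = 81% | 471/771 = 61% |
| 1,102 | 952/1,102 = 86% | 802/1,102 = 73% |

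If a same-center sub-study was intended, T = k and s = 0.

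**Illustration only.** Let g be the gap in mean LA change, apart from any treatment effect, between ablation patients at other centers and those at the selected centers. The bias is s × g. With g = 0.1 SD (assumed), it runs from 0.094 × 0.1 = 0.009 SD to 0.864 × 0.1 = 0.086 SD. The standard errors, √(1/150 + 1/T), are 0.098 (T = 331) and 0.087 (T = 1,102), so the bias is about 0.1 to 1.0 standard errors. No document supplies g.

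**Precision cost of restricting.** The difference detectable with 80% power at two-sided 5% is 2.80 × √(1/150 + 1/n) SD, where n is the number of ablation patients. This takes all 150 drug patients as having both scans.

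- Pooled: 0.28 (n = 331), 0.25 (n = 771), 0.24 (n = 1,102).
- Restricted: 0.32 (n = 150), 0.28 (n = 300).

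**The case against.** **A same-center sub-study may be what was meant.** Protocol 8.2.4 opens by placing the imaging at a subset of sites without separating the arms, and 4.4.1 rests its randomization claim on centers that scan both arms. SAP 9.13 then refers to sub-study participants. This is a plausible reading, and under it the center problem disappears. It is not written into the analysis, however, and 5.3.1 and the routine-scan rule in 4.4.1 point the other way.

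**Other safeguards exist.** Baseline adjustment and a single image analysis lab limit center differences, and SAP 9.13 allows further covariates. That adjustment is conditional on differences appearing, and site is not named.

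**Lesion extent is not bias.** A reader might infer that wider lesions at other centers, which 5.3.2 permits, would produce false positives. The documents do not support that. Such variation acts only on ablated patients and belongs to the effect of the strategy being compared. It is effect heterogeneity, not an error under a true null.

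**For-cause scans.** A reader might also infer that scanned ablation patients over-represent AF recurrences by a calculable amount. The only indication the protocol names is PV stenosis, and the 24% recurrence rate in its background section is a 12-month figure, whereas the follow-up scan falls between 90 days and 6 months. No reliable figure follows.

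**Missing data.** SAP 9.13 does promise to describe completeness. With one follow-up measurement, a likelihood-based analysis using only the baseline value adds little to the planned model. Both points stand and reduce the weight of the omission, but the SAP still departs from protocol 8.2.4 without explanation.

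**Conclusion.** The concern holds as a gap in the analysis population and model. As written, SAP 9.13 permits a comparison of drug patients from selected centers with ablation patients from a wider set, which would not carry the benefit claimed in 4.4.1. The missing-data discrepancy holds however the sub-study is read.

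The documents do not show that the comparison is non-randomized, nor do they support any particular false-positive rate. The share from other centers could be 0% or as high as 86%, depending on an undefined population and on counts that are assumed here. Any error rate would also need a center gap that nobody has stated.

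Severity is minor. The endpoint is mechanistic, and the primary and clinical secondary endpoints do not depend on it.

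**What to change.** In SAP 9.13:

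1. Define the between-arm population as patients of both arms randomized at the centers committed to scanning all enrolled patients, analyzed by randomized arm.
2. Fit the linear model with the baseline value and site, which is the randomization stratum.
3. Report, for each arm, the number with both scans out of the number randomized at those centers.
4. Use ablation scans from other sites only to describe change within the ablation arm.
5. Restore at least one missing-data sensitivity analysis from protocol 8.2.4.

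Align protocol 5.3.1 with this definition.

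The change needs one population sentence, one model term, one completeness table and one sensitivity analysis, all from imaging already planned. The price is fewer ablation patients. Under the assumptions above, the difference detectable with 80% power rises from 0.24–0.28 SD to 0.28–0.32 SD, and the result describes centers that scan both arms.

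Restriction does not remove selection within an arm. Drug patients are asked after randomization and may decline, so the report should state this limitation.
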